Brief Title: GER Poses a Potential Risk for Late Complications of BPD

Official Title: Gastroesophageal Reflux Really Pose a Potential Risk for Late Complications of Bronchopulmonary Dysplasia in Extremely Premature Infants

Identifiers: NCT03014453

Unique Protocol ID: A333-1

Sponsor: Shengjing Hospital

Investigator: [name]

Official Title: Professor

Affiliation: Shengjing Hospital

Study Start: July 1, 2017

Document Date: March 24, 2020

Study Protocol

Research background

Bronchopulmonary dysplasia (BPD) is a common condition in the low birth weight infants. Although most of the BPD symptoms improved after a regular treatment in infancy, there are still a few late complications left such as the frequent respiratory symptoms, a slower weight gain and even sudden death. These late complications have made so much trouble to the healthcare of BPD infants. How to find the risk factors and to reduce the prevalence of these late symptoms becomes necessary. In this study, a cohort of BPD infants was observed with the late complications obtained by a monthly followed up for 18 months after discharge, the prevalence and risk factors were analyzed via logistic regression, calculating odd ratios (OR) and 95% confidence intervals. As one of the risk factors, GER was verified whether to play a critical role in these late complications.

Research purposes

A prospective cohort study is carried out to explore the potential risk of gastroesophageal reflux as a late complication of bronchopulmonary dysplasia in preterm infants.

Methods

Patients

The study was approved by the Ethics Committee of China Medical University. Written consent was obtained from the parents. The cohort included infants born at or before 32 weeks gestational age (GA) with BPD between January 2017 and July 2018 at Shengjing Hospital of China Medical University, the First Hospital of Jilin University, and Shanghai General Hospital of Shanghai Jiao Tong University. BPD was diagnosed at 36 weeks postmenstrual age (PMA) on the National Heart, Lung and Blood Institute classification and categorized as “mild, moderate or severe”. Infants with no BPD, severe gastrointestinal malformations and refused GER monitoring were excluded.

Detailed information on the BPD infants, including age, sex, Apgar scores, treatments after

born, clinical symptoms, and other clinical information we designed. After discharge, all the patients received a regular follow up for late complications including respiratory symptoms (including home respiratory support, respiratory medication administration, cough without cold at least once per week, re-hospitalization due to respiratory diseases), vomiting when feeding, hypoxic ischemic injury, retinopathy of prematurity, rehospitalization and sudden death.

Measurements and definitions

Respiratory morbidity included pneumonia, respiratory medication administration for dyspnea, cyanosis and intermittent apnea, and cough without cold at least once per week. Vomiting when feeding referred to vomiting at least once a week and retinopathy of prematurity were diagnosed by local doctors. The diagnoses of hypoxic-ischemic injury mainly depend on MRI.

pH-MII methods

A 24h pH-MII measurement was carried out twice in each infant in the study group of 116 infants with BPD. The first test was performed at 36 weeks PMA and the second, at the last interview between the 17th and 18th month of PMA. Pathological GER was diagnosed when both the tests were positive for GER. In pH-MII monitoring, the probe (Kanglian, Beijing, China) had eight impedance channels (Z1-Z6) and two pH channels. The probe was inserted transnasally into the esophagus. The proximal pH channel was positioned 3 cm above the left diaphragm and the distal pH channel was positioned in the stomach. The position of the pH channels was verified by chest radiography. The data were evaluated using the manufacturer's software and each trace was manually reviewed by the same operator. This operator was not informed of the final outcome.

GER was diagnosed based on the proximal pH channel. Reflux index (RI), which is the percentage of the total recording time with an esophageal pH < 4, was used to categorize pathological GER. Acid GER was defined by a RI > 12, irrespective of the impedance value. Weak acid reflux was defined as a pH between 4–7 when the impedance value decreased > 20% from the baseline while the duration of intragastric pH > 4 for < 70% of the time. DGER was diagnosed for RI < 12 with decreasing impedance and when the intragastric pH > 4 for > 70% of the time. GER without acid GER and DGER was regarded as non GER.

Determination of gastric sodium ions

The gastric juice was sampled from 89 infants. All medications were forbidden 24 hours prior to sample collection. A feeding tube was always placed for daily meals. Gastric juice was taken for 30 minutes via the feeding tube before meal at 2AM, 10AM and 6PM in a given day with an interval of 8 hours, and was analyzed on a rapid ion analyzer (BHF-II, Bairikang, Beijing). Each patient was sampled three times and a Na⁺ concentration > 50 mmol/L in all three samples was considered positive.

Statistics

Continuous variables were graded as categorical variables and the categorical variables were expressed as frequency and percentage. Chi-square test was used to compare categorical differences. Adjusted odds ratios (ORs) and corresponding 95% confidence intervals (CIs) for every late complication of BPD were estimated separately with multiple logistic regression models (forward). Potential confounders included gender, GA (< 30 weeks and \geq 30 weeks), birth weight (< 1500 g and > 1500 g), Apgar score, invasive ventilation (< 7 days and \geq 7 days), pulmonary surfactant, caffeine, ventilator-associated pneumonia, and GER were

adjusted. All computations relied on standard software (SPSS v19.0; SPSS Inc, Chicago, IL, USA), and statistical significance was set at $P < 0.05$.

Results

Prevalence of Late Complications

Among the 116 infants with BPD in the final cohort, late complications occurred in 74 infants with an overall prevalence of 63.79%. These complications included respiratory symptoms in 49.14% (n=57) infants, including pneumonia (n=10, 8.62%); dyspnea, cyanosis and intermittent apnea warranting respiratory medication administration (n=25, 21.55%), and cough (n=44, 37.93%). Vomiting occurred in 45 (38.79%), ROP in 30 (25.86%), and hypoxic-ischemic injury in 4 (3.45%) infants. One (0.86%) infant suffered sudden infant death syndrome. Re-hospitalization was recorded in 31 (26.72%) infants.

GER Prevalence in BPD

Pathological GER occurred in 49 infants with BPD with an overall prevalence of 42.24%, including acid GER (n=21, 18.10%) and DGER (n=28, 24.14%). SI, SSI, and SAP measurements were $> 99\%$ in all 49 infants, confirming the association between reflux events and symptoms. Weak acid GER was found in almost all infants including those with acid GER, DGER and non GER. The percentage of weak acid GER events over the overall reflux episodes varied from 40.74–100%, and there was no significant difference among infants with acid GER, DGER and non GER. In the evaluation of DGER, 33 infants are positive for pH-MII monitoring, and gastric $\text{Na}^+ > 50$ mmol/L was noted in 28 infants who were finally diagnosed as DGER. Five infants positive for pH-MII and negative for gastric $\text{Na}^+ > 50$ mmol/L were diagnosed as weak acid GER. No infants negative for pH-MII and positive for

gastric $\text{Na}^+ > 50 \text{ mmol/L}$ were noted. Among the BPD infants, the prevalence of acid GER and DGER was 12% and 17.33% in mild BPD, 32.14% and 32.14% in moderate BPD, and 23.08% and 46.15% in severe BPD individually. Among the 74 symptomatic infants, the prevalence was 14.66% and 21.55%.

Risk Factors for Late Complications

Accordingly, risk factors for respiratory symptoms were $\text{GA} \leq 30$ weeks (odds ratio, OR=3.213; 95% CI, 1.221-8.460), birth weight $< 1500 \text{ g}$ (OR=2.803; 95% CI, 1.014-7.749), invasive ventilation > 7 days (OR=4.952; 95% CI, 1.508-16.267), acid GER (OR=4.630; 95% CI, 1.305-16.420), and DGER (OR=5.588; 95% CI, 1.770-17.648). Risk factors for vomiting were $\text{GA} \leq 30$ weeks (OR=5.813; 95% CI, 2.424-13.940), acid GER (OR=3.394; 95% CI, 1.107-10.403), and DGER (OR=4.379; 95% CI, 1.552-12.354). Risk factors for ROP were $\text{GA} \leq 30$ weeks (OR=8.741; 95% CI, 3.203-23.851), while the major risk factors for re-hospitalization were $\text{GA} \leq 30$ weeks (OR=3.894; 95% CI, 1.405-10.791), acid GER (OR=5.866; 95% CI, 1.640-20.972), and DGER (OR=8.436; 95% CI, 2.697-26.382).

Conclusion

In summary, the prevalence of late complications of BPD is high; pediatricians should pay great attention to BPD infants after discharge to reduce the damage caused by these late complications. GER, or rather DGER, is a potential risk for the late complications of BPD.

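### Weekly vomiting may be a sign of the reflux under study, so its two GER odds ratios are not independent evidence that GER raises the risk of late complications of BPD

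*Combined protocol and SAP*

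**What the plan says.** In Methods (Patients), the follow-up outcomes are respiratory symptoms together with "vomiting when feeding, hypoxic ischemic injury, retinopathy of prematurity, rehospitalization and sudden death". Measurements and definitions then states: "Vomiting when feeding referred to vomiting at least once a week". No cause of the vomiting is recorded or excluded.

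The exposure is set in pH-MII methods. Each infant was tested twice, first at 36 weeks PMA and then "at the last interview between the 17th and 18th month of PMA". Both results count: "Pathological GER was diagnosed when both the tests were positive for GER". Results (GER Prevalence in BPD) shows that gastric sodium was also used to settle the DGER diagnosis.

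Statistics specifies a separate forward logistic model for each complication, with GER among the candidate covariates. In Results (Prevalence of Late Complications), "late complications occurred in 74 infants with an overall prevalence of 63.79" per cent, and 45 infants had vomiting. In Results (Risk Factors for Late Complications), the vomiting model gives "acid GER (OR=3.394; 95% CI, 1.107-10.403), and DGER (OR=4.379; 95% CI, 1.552-12.354". The Conclusion then names GER, and DGER in particular, as a potential risk for late complications taken as a group.

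**The concern.** The study asks whether reflux is a risk factor for what happens to BPD infants after discharge. Reflux is gastric content entering the oesophagus, and vomiting is gastric content being brought up. If some of the recorded vomiting is simply reflux showing itself, GER and vomiting will be associated even when reflux has no effect on the course of BPD.

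The timing of the exposure makes this harder to dismiss. An infant belongs to the GER group only if the second test, at the end of follow-up, is also positive. GER status is therefore settled after the vomiting has been observed, and the group is limited to infants who still reflux at that point.

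Two things are at stake. The Conclusion draws on three outcomes associated with GER, and one of them may partly restate the exposure. The any-complication prevalence also includes an unknown number of infants who may qualify only through that outcome. The documents do not discuss the overlap and give no result without vomiting.

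**Working it through.** **Inputs.** From Results (Prevalence of Late Complications), n = 116: any complication 74, respiratory symptoms 57, vomiting 45, ROP 30, re-hospitalization 31, hypoxic-ischemic injury 4, sudden death 1. From Results (GER Prevalence in BPD): pathological GER 49 (acid 21, DGER 28). The odds ratios come from Results (Risk Factors for Late Complications).

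**1. Reported proportions.** 74/116 = 63.79%, 57/116 = 49.14% and 45/116 = 38.79%. All match the text.

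**2. The GER odds ratios.** Three outcomes by two GER types give six. For a Wald interval, the odds ratio should equal √(lower × upper).

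| Outcome | GER type | Reported OR | √(lower × upper) |
|---|---|---|---|
| Respiratory | acid | 4.630 | √(1.305 × 16.420) = 4.629 |
| Respiratory | DGER | 5.588 | √(1.770 × 17.648) = 5.589 |
| Vomiting | acid | 3.394 | √(1.107 × 10.403) = 3.394 |
| Vomiting | DGER | 4.379 | √(1.552 × 12.354) = 4.379 |
| Re-hospitalization | acid | 5.866 | √(1.640 × 20.972) = 5.865 |
| Re-hospitalization | DGER | 8.436 | √(2.697 × 26.382) = 8.435 |

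All six agree within rounding, so the question is what the two vomiting figures mean and not whether they are computed correctly. With SE = (ln upper − ln lower)/3.92 and z = ln OR/SE, vomiting gives z = 2.138 (two-sided p = 0.033) for acid GER and z = 2.791 (p = 0.005) for DGER.

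**3. Prevalence without vomiting.** The number of infants with at least one non-vomiting complication is bounded by:
- lower: max(57, 30, 31, 4, 1) = 57
- upper: min(74, 57 + 30 + 31 + 4 + 1) = min(74, 123) = 74

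The prevalence is therefore between 57/116 = 49.14% and 74/116 = 63.79%. Vomiting-only infants number between 74 − 74 = 0 and 74 − 57 = 17, which is at most 17/74 = 23.0% of those counted as having a complication.

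**4. What remains.** Each complication has its own model, and vomiting is not among the covariates listed in Statistics. Setting the vomiting model aside therefore leaves 4.630, 5.588, 5.866 and 8.436 as reported, all with intervals excluding 1.

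**5. How far exposure and outcome coincide.** The 14.66% and 21.55% given for the 74 symptomatic infants match 17/116 and 25/116; over 74, the same counts would be 22.97% and 33.78%. On that reading, 17 + 25 = 42 GER infants had a complication. Then at least 45 − 42 = 3 vomiting infants had no pathological GER, and at least 49 − 42 = 7 GER infants did not have the vomiting outcome.

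**The case against.** A reader might infer that the vomiting analysis is circular. The documents do not support that. GER is defined by pH-MII, with gastric sodium for DGER, and vomiting is in no criterion. The operator who reviewed the traces was not told the outcome. On the reading in step 5 of the working, the two groups differ in both directions. The vomiting odds ratios are also the smallest of the three outcomes for both GER types, and gestational age has a larger estimate (5.813) in the same model. All of this stands against circularity.

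It does not remove the overlap. Weak acid reflux was found in almost all infants, including those classed as non GER, so vomiting in the reference group can pull the odds ratio towards 1. The intervals also overlap widely. The size of the odds ratio does not settle the matter either way.

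Two passages look like support but carry little weight. The Background says "there are still a few late complications left such as the frequent respiratory symptoms, a slower weight gain and even sudden death". That omits vomiting, but the list is illustrative and also omits ROP, hypoxic-ischemic injury and re-hospitalization. The symptom-index sentence, "confirming the association between reflux events and symptoms", does not name the symptoms and could apply equally to respiratory ones.

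A reader might also extend the point to re-hospitalization. No passage mentions admission for vomiting or reflux work-up. Attendance for pH-MII cannot explain that outcome, since all 116 infants were tested twice and only 31 were re-hospitalized.

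Finally, the premise that vomiting can be a sign of reflux is clinical knowledge that the documents do not state.

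**Conclusion.** The point holds as one of overlapping constructs. Two of the six GER odds ratios (3.394 and 4.379) should not count as independent support for the GER objective. The conclusion assumes that vomiting at feeds can be a clinical sign of reflux; the documents neither state nor exclude this, and the outcome definition does nothing to separate the two.

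The effect on the any-complication figure is bounded but unknown: 0 to 17 infants, or a prevalence between 49.14% and 63.79%. A reader might infer that the reported 63.79% is inflated. That is not shown, because ROP or re-hospitalization could account for all 17.

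Nor do the documents claim that GER brings the complications about; they speak of risk factors and a potential risk. That cautious conclusion can still draw on the respiratory and re-hospitalization models, whose four odds ratios this point leaves untouched.

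**What to change.** - Report vomiting separately as a possible clinical feature of GER. Its association with GER can still be shown, labelled as descriptive, but should not be cited for the GER objective.
- Restate the any-complication prevalence and the count of symptomatic infants without vomiting, beside the current figures.
- Give the number of vomiting-only infants by GER status (acid, DGER, none).
- Rest the GER conclusion on the non-vomiting outcomes, and note that GER status depends on a test at the end of follow-up.

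The cost is a re-tabulation of data already collected; no model has to be refitted. The headline prevalence may fall, to no less than 49.14%, and GER would be reported as a risk factor for two outcomes instead of three.

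### Retinopathy of prematurity and hypoxic-ischemic injury count as late complications with no new-onset condition, so 0 to 17 of the 74 affected infants may qualify through these two diagnoses alone

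*Combined protocol and SAP*

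**What the plan says.** The Research background describes "late complications obtained by a monthly followed up for 18 months after discharge". The list of outcomes followed after discharge, given under Methods, includes "vomiting when feeding, hypoxic ischemic injury, retinopathy of prematurity, rehospitalization and sudden death".

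Measurements and definitions then sets the case rules. For ROP it says that "retinopathy of prematurity were diagnosed by local doctors". For brain injury it says: "The diagnoses of hypoxic-ischemic injury mainly depend on MRI". No examination date, MRI date, baseline status or onset condition is given for either. The exclusions in the Patients section are absence of BPD, severe gastrointestinal malformation and refusal of GER monitoring. Existing ROP or hypoxic-ischemic injury is not among them.

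On exposure, the pH-MII methods section states: "The first test was performed at 36 weeks PMA and the second, at the last interview between the 17th and 18th month of PMA". An infant is classed as having pathological GER only if both results are positive.

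Under Prevalence of Late Complications the results give "ROP in 30 (25.86%), and hypoxic-ischemic injury in 4 (3.45%) infants" as parts of a composite of 74 out of 116 infants.

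**The concern.** Cough and vomiting are defined by a weekly frequency, so a follow-up interview records a current symptom. ROP and MRI-diagnosed injury are different: once made, the diagnosis stands. A diagnosis from the neonatal stay can be recorded at a post-discharge visit and would meet the definition as written. Without a date or a baseline examination, new disease cannot be told from old.

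Three reported items depend on this. The first is the 63.79%, which supports the first conclusion, that late complications are common after BPD. The second is the group of 74 symptomatic infants, for whom GER frequencies are quoted. The third is the ROP model, because the Statistics section fits a separate logistic model, with GER among the covariates, for each late complication. For ROP and hypoxic-ischemic injury the order of GER and outcome cannot be established from what is recorded.

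**Working it through.** **Inputs**, all from Prevalence of Late Complications: cohort 116; any late complication 74; respiratory symptoms 57; vomiting 45; re-hospitalization 31; ROP 30; hypoxic-ischemic injury 4; sudden infant death 1.

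**Reproducing the plan's figures.**
- Composite: 74/116 = 63.79%, as printed.
- ROP: 30/116 = 25.86%, as printed.
- Hypoxic-ischemic injury: 4/116 = 3.45%, as printed.

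**Bounds without the two conditions.** Let U be the number of infants with at least one complication other than ROP or hypoxic-ischemic injury.
- Lower bound: U is at least the largest other component, max(57, 45, 31, 1) = 57.
- Upper bound: U is at most the composite count, 74.
- Infants counted only through ROP or hypoxic-ischemic injury: 74 − U, which runs from 74 − 74 = 0 to 74 − 57 = 17.
- Composite without the two conditions: from 57/116 = 49.14% to 74/116 = 63.79%. The largest possible fall is 17/116 = 14.66 percentage points.

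**Both ends are attainable.** U = 57 requires every infant with vomiting, re-hospitalization or sudden death to be among the 57 with respiratory symptoms. The 30 + 4 = 34 diagnoses are then enough to cover the other 17. U = 74 requires the 17 infants without respiratory symptoms to have some other complication. The 45 with vomiting are enough to cover them all.

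**Illustration.** The number counted only through the two conditions is an assumption here, because the overlap between complications is not reported.

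| Counted only through ROP or hypoxic-ischemic injury | Remaining | Composite |
|---|---|---|
| 0 | 74 | 63.79% |
| 5 | 69 | 59.48% |
| 10 | 64 | 55.17% |
| 17 | 57 | 49.14% |

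These rows drop both conditions entirely. A composite that drops only the pre-existing cases cannot be lower than the matching row, and it needs the diagnosis dates.

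**Reach into the models.** Under Risk Factors for Late Complications, GER terms are reported for respiratory symptoms, vomiting and re-hospitalization. The ROP model reports gestational age only (OR 8.741; 95% CI 3.203 to 23.851). No model is reported for hypoxic-ischemic injury. The published GER odds ratios therefore rest on neither condition.

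**The case against.** The strongest reply is that both conditions are listed under follow-up after discharge, and that naming who makes the ROP diagnosis does not cancel that frame. This is fair as a statement of intent. But the frame says when information was collected, not when disease began, and nothing else in the text separates the two.

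A second reply is that the figure is called a prevalence, a term that ordinarily includes existing disease. That stands in part: counting existing cases is a legitimate choice if it is stated. It fits poorly with the label of late complications, and the choice is not stated.

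A reader might go further and infer any of the following. The documents support none of them.
- *Cases from the neonatal unit were in fact counted.* No dates are given, so this is possible under the rule but not shown.
- *GER cannot be a risk factor for a condition diagnosed before the 36-week test.* First measurement is not onset, and reflux may have begun earlier. What can be said is that the order is unknown.
- *The GER findings are undermined.* The reported GER odds ratios use other outcomes.
- *The true composite is 49.14%.* That is one end of a range whose other end is no change at all.

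**Conclusion.** The point holds as a gap in the outcome definitions with a bounded effect, not as a demonstrated miscount. Between 0 and 17 of the 74 infants could be in the composite only because of ROP or hypoxic-ischemic injury, so the prevalence without them lies between 49.14% and 63.79%. The bounds use only the printed counts and assume that the 74 is the union of the listed complications.

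The composite, the symptomatic group and the ROP model are exposed. The GER associations reported for respiratory symptoms, vomiting and re-hospitalization are not. Even the lower end would not clearly overturn the statement that prevalence is high, since the plan sets no threshold for it.

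An onset rule would not fully restore temporal order. GER status also depends on the second test at the 17th to 18th month, so exposure is not settled at 36 weeks for any outcome. This is a cheap improvement. It is more than a missing detail, because results are already reported with no split of new from existing disease.

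**What to change.** 1. Report the composite prevalence and the symptomatic-group figures with and without ROP and hypoxic-ischemic injury. This needs only the existing data set. State the denominator for the symptomatic group: the printed 14.66% and 21.55% equal 17/116 and 25/116, whereas over 74 the same counts give 22.97% and 33.78%.
2. Where first-diagnosis dates can be found in existing records, classify cases diagnosed before discharge as baseline comorbidities. Discharge is the plan's own boundary for late complications. These infants stay in the 116 for the composite, because they can still develop other complications.
3. Refit the ROP model on new cases only, leaving out infants with ROP at baseline rather than coding them as non-events.
4. State that the order of GER and these two outcomes is not established, and that the two-test exposure rule limits what an onset rule can repair.

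The cost is a look-up of dates and a recount. The documents do not say that the dates are available, so this is an assumption; step 1 can be done without them. The downside is a possibly lower headline prevalence and fewer than the present 30 ROP events, hence a less precise ROP model.

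### Three hospitals recruited infants, but hospital is in no model and no by-hospital result is given, so the GER odds ratios may be biased in either direction

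*Combined protocol and SAP*

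**What the plan says.** The Patients section places the cohort "at Shengjing Hospital of China Medical University, the First Hospital of Jilin University, and Shanghai General Hospital of Shanghai Jiao Tong University". Measurements and definitions sets a weekly threshold for vomiting and, in the same sentence, says that "retinopathy of prematurity were diagnosed by local doctors". Local diagnosis certainly applies to ROP, and the sentence may or may not be meant to cover vomiting as well. Nothing is said about who recorded the respiratory outcomes or readmissions, or whether a common rule was used across hospitals.

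The Statistics section fits one logistic model per late complication, with forward selection. The candidate list opens with "Potential confounders included gender, GA" and goes on to birth weight, Apgar score, invasive ventilation, surfactant, caffeine, ventilator-associated pneumonia and GER. Hospital is not on it. No stratification, clustering adjustment or random effect is described, and the Results contain no count by hospital.

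On the exposure side, the pH-MII section says that one operator, unaware of the final outcome, reviewed every trace. Gastric sodium, which confirmed DGER, was measured in 89 of the 116 infants. Infants whose families refused GER monitoring were excluded.

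Under Risk Factors for Late Complications, GER odds ratios are reported for respiratory symptoms, vomiting and re-hospitalization. For ROP the only reported risk factor is gestational age.

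**The concern.** Hospital confounds a GER odds ratio if two things are true together: the outcome rate differs by hospital, and GER prevalence differs by hospital, beyond what the covariates in the model explain.

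Both are plausible here. Respiratory symptoms include use of respiratory medication, and re-hospitalization is itself an admission decision, so prescribing and admission thresholds may enter these outcomes. Vomiting depends on how it was asked about and recorded. GER prevalence may differ through case mix, through who refused monitoring, and through which infants had gastric sodium measured. The documents do not say that any of these differed between hospitals, but they give nothing from which a reader could check.

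At stake is the main conclusion, that GER, and DGER in particular, is a potential risk for late complications. If high-GER hospitals also record more symptoms, pooling inflates the odds ratio. If they record fewer, it hides part of a real effect. Pooling also treats infants from the same hospital as no more alike than infants from different ones.

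**Working it through.** **Inputs.** Cohort 116; respiratory symptoms 57, vomiting 45, ROP 30, re-hospitalization 31 (Prevalence of Late Complications). Pathological GER 49, of which acid 21 and DGER 28 (GER Prevalence in BPD). Odds ratios and intervals from Risk Factors for Late Complications. No by-hospital figure exists, so the site scenarios below are assumptions.

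**Stated figures reproduced.** 49/116 = 42.24%; 57/116 = 49.14%; 45/116 = 38.79%; 31/116 = 26.72%. All agree with the document.

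**Odds ratio produced by site alone.** Assume three equal sites and no association between GER and outcome within any site. One site lies at the overall rates; the other two lie d points above and below for both GER and outcome. Let g and q be the overall GER and outcome proportions. Pooling gives:

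- C = ±(2/3) × d × d, positive if the high-GER site is also the high-outcome site (aligned), negative if it is the low-outcome site (opposed)
- a = g × q + C (GER and outcome); b = g − a; c = q − a; e = 1 − g − q + a
- pooled OR = (a × e)/(b × c)

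For any-GER and respiratory symptoms, g = 0.4224, q = 0.4914 and g × q = 0.2076:

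| d | Pattern | C | a | b | c | e | OR |
|---|---|---|---|---|---|---|---|
| 0.10 | aligned | 0.0067 | 0.2142 | 0.2082 | 0.2771 | 0.3004 | 1.12 |
| 0.20 | aligned | 0.0267 | 0.2342 | 0.1882 | 0.2571 | 0.3204 | 1.55 |
| 0.10 | opposed | −0.0067 | 0.2009 | 0.2215 | 0.2905 | 0.2871 | 0.90 |
| 0.20 | opposed | −0.0267 | 0.1809 | 0.2415 | 0.3105 | 0.2671 | 0.64 |

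The same formula with aligned differences of ±10 and ±20 points gives 1.12 and 1.58 for vomiting (q = 0.3879), and 1.15 and 1.74 for re-hospitalization (q = 0.2672). If GER prevalence is the same at every site, C = 0 and the odds ratio is 1.00.

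**Could case mix move GER prevalence?** The percentages by BPD severity fit 75 mild, 28 moderate and 13 severe infants. This is a back-calculation: acid GER 9 + 9 + 3 = 21 and DGER 13 + 9 + 6 = 28, both matching the stated totals. Any-GER is then 22/75 = 29% in mild BPD and (18 + 9)/41 = 66% in moderate or severe BPD. BPD severity is not a covariate either. Through severity alone, a 10-point shift in GER prevalence needs a shift in the mild share of about 10/(65.9 − 29.3) = 27 percentage points. Small differences in severity mix would therefore not be enough, but large ones could be.

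**Against the reported results.** Point estimates and lower limits for GER are:

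| Outcome | Acid GER | DGER |
|---|---|---|
| Respiratory symptoms | 4.630 (lower limit 1.305) | 5.588 (1.770) |
| Vomiting | 3.394 (1.107) | 4.379 (1.552) |
| Re-hospitalization | 5.866 (1.640) | 8.436 (2.697) |

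The most extreme scenario tried, ±30 points in GER and ±25 in outcome, aligned (C = (2/3) × 0.30 × 0.25 = 0.05), gives 2.30 for respiratory symptoms, 2.38 for vomiting and 2.85 for re-hospitalization. Each is below the smaller GER estimate for that outcome.

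**Room for hospital in the models.** Counting eight single-parameter covariates plus two for GER type gives about 10 candidate parameters, or 12 with hospital. Events per candidate parameter fall from 57/10 = 5.7 to 57/12 = 4.8 (respiratory), from 45/10 = 4.5 to 45/12 = 3.8 (vomiting), and from 31/10 = 3.1 to 31/12 = 2.6 (re-hospitalization).

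**The case against.** Five points can fairly be made on the other side.

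- **Exposure reading was standardised.** One operator, blind to outcome, reviewed every trace, and probe position was checked by radiograph. This stands, and it weakens the idea that some hospitals simply found more GER. It does not touch case mix, refusal of monitoring, or selection of the 89 infants with gastric sodium.
- **Case mix is partly covered.** Gestational age, birth weight, ventilation, surfactant, caffeine and ventilator-associated pneumonia are candidates. This stands in part: forward selection may drop any of them, and none measures prescribing, admission or recording practice.
- **Local variation in practice is an inference.** Correct. The document describes local diagnosis for ROP only, or at most for ROP and vomiting. A reader might infer from "retinopathy of prematurity were diagnosed by local doctors" that local ROP diagnosis has been turned into a GER effect. The document does not support that, because it reports no GER effect for ROP.
- **The illustration shows scale only.** It is crude, uses any-GER at 42.24%, and assumes equal sites whose ranks align or oppose perfectly. A figure of ±20 points means a 40-point gap between the outer sites on both variables. The lowest reported limits are adjusted and belong to acid GER, whose prevalence is 18.10%, so a site 20 points below that is impossible. The illustration should not be used to divide down a confidence limit.
- **Events are few.** Adding hospital to models this thin has a real cost, which the fix has to allow for.

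**Conclusion.** The point stands as a cheap improvement. Hospital is a design feature of a three-hospital cohort, it is missing from every model, and no by-hospital data let a reader judge whether that matters. The GER odds ratios for respiratory symptoms, vomiting and re-hospitalization can therefore be biased up or down by an unknown amount. The blinded single reader and the listed covariates reduce the risk without removing it.

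Under the assumptions stated, site alone gives about 1.12 to 1.55 for respiratory symptoms when differences are aligned and about 0.90 to 0.64 when they are opposed. Effects of that order could matter for the weaker GER results, those whose lower limits lie nearest 1.

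Two stronger readings are not supported. One is that the GER association is a product of pooling hospitals: no scenario tried reaches the estimates of 3.4 to 8.4. The other is that the bias must inflate the effect: opposed differences of the same size would mask it, and nothing in the document indicates which applies.

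**What to change.** 1. Tabulate, by hospital, the number of infants, BPD severity, acid GER, DGER, gastric sodium sampling, and each late complication.
2. Refit the respiratory, vomiting and re-hospitalization models with hospital forced in, not left to forward selection, either as a fixed factor or as the stratum in conditional logistic regression. With only three sites, one of these is preferable to a random effect.
3. Because there are only 31 to 57 events per model, use a reduced covariate set fixed in advance, or a penalised fit. Fit that same set with and without hospital, so that any change in the GER odds ratios can be attributed to hospital and not to the changed covariates.
4. State whether the GER conclusion holds.

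This needs no new data if, as is to be expected, each infant's recruiting hospital is on file. The fixed factor costs 2 degrees of freedom. Stratification estimates no site parameters but gives up between-hospital information, and a hospital where all or none of the infants had the outcome would contribute nothing. Either way, somewhat wider intervals should be expected.
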